5. TREATMENT OF PATIENTS

5.1. Drugs Administered During the Study

IMP (see Section 3.8) will be administered as oral tablets at a starting dose of 6 mg. Titration schemes based on body weight at baseline are shown in [Table 2](#). The maximum daily dose is determined by body weight and CYP2D6 impairment status at baseline. Although dose adjustments can be made up to and including the week 7 telephone call, if a stable dose is reached before then, the patient should continue taking that dose for the remainder of the titration period and throughout maintenance dosing. If a patient experiences a “clinically significant” adverse event that is attributed to the IMP, the investigator will determine if a dose reduction or suspension is necessary. At the end of the titration period, the patient’s dose will be established for the maintenance period. If a patient experiences an adverse event during the maintenance period and the investigator believes a dose reduction is warranted, the dose may be reduced.

IMP will be dispensed in the clinic. Patients will receive doses for 2 weeks at baseline, week 2, and week 4 visits (current dose level and next dose level) to cover the telephone contacts. At week 6 and week 9 visits, patients will receive doses for 3 weeks.

IMP will be administered as follows:

- IMP should be swallowed whole and taken with food. Tablets should be taken with food (eg, a snack) and should not be taken on an empty stomach.
- Dosing will be based on body weight and CYP2D6 impairment status at the baseline visit, as shown in [Table 2](#).
- The starting dose is 6 mg in all patients. Daily doses will be administered twice daily, approximately 8 to 10 hours apart during the day. A minimum of 6 hours should elapse between doses. If a patient misses a dose and it is within 6 hours of their next dose, the missed dose should be skipped.
- After week 1, dose increases may not occur more frequently than every 5 days.
- Dose reductions, if required, should be in increments of 6 mg. **If more than 1 dose reduction is required for an adverse event, the medical monitor must be notified.**
- During the titration period, the dose of the IMP will be adjusted weekly according to [Table 2](#) to identify a dose level that optimally reduces tics and is well tolerated. Investigators will be blinded to CYP status, with a dose cap for poor metabolizers prespecified by the IRT.

IMP will be packaged in blister packs and provided for patients to take at home (see Section 3.8).

Table 2: Maximum Daily Dose of IMP by Study Day and Weight Category at Baseline

Study day ^a	Weight category					
	20 to <30 kg		30 to <40 kg		≥40 kg	
CYP impairment status	Not impaired	Impaired	Not impaired	Impaired	Not impaired	Impaired
Day 1-7	6 mg	6 mg	6 mg	6 mg	6 mg (Days 1 and 2) 12 mg ^b	6 mg (Days 1 and 2) 12 mg ^b
Day 8-14	12 mg	12 mg	12 mg	12 mg	18 mg	18 mg
Day 15-21	18 mg	18 mg	18 mg	18 mg	24 mg	24 mg
Day 22-28	18 mg	18 mg	24 mg	24 mg	30 mg	30 mg
Day 29-35	24 mg	18 mg	30 mg	24 mg	36 mg	36 mg
Day 36-42	24 mg	18 mg	36 mg	24 mg	42 mg	36 mg
Day 43-49	30 mg	18 mg	42 mg	24 mg	48 mg	36 mg

^a Administration of a given dose will take place throughout the days indicated. The new dose starts the morning after the telephone contact or the morning after the clinic visit (ie, Days 8, 15, 22, 29, 36, and 43), as applicable.

^b Patients will receive 6 mg on days 1 and 2, and 12 mg starting on day 3.

bid=twice a day; CYP=cytochrome P450; IMP=investigational medicinal product.

Note: CYP impaired patients are those patients who are receiving a strong CYP2D6 inhibitor or who are a CYP2D6 poor metabolizer. The investigator, in consultation with the patient and caregiver/adult, will determine if a dose increase is warranted to achieve optimal tic reduction.

5.2. Restrictions

Medications prohibited before and/or during the study are described in Section 5.3.

While patients receiving strong CYP2D6 inhibitors such as paroxetine, fluoxetine, and bupropion at baseline may be enrolled into this study, the addition or removal of strong CYP2D6 inhibitors during treatment is discouraged as this would have an effect on exposure to active circulating drug. If the addition or removal of a strong CYP2D6 inhibitor is required from a clinical perspective, the medical monitor should be contacted so an appropriate change in IMP can be made. The use of quinidine and terbinafine are prohibited (see Appendix A, Table 8).

Restrictions in regard to sexual activity and required laboratory values are provided in the inclusion and exclusion criteria.

As with other VMAT2 inhibitors (tetrabenazine, reserpine), patients should be advised that the concomitant use of alcohol or other sedating drugs with TEV-50717 may have additive effects and cause or worsen somnolence. Given the age of the study population, the use of alcohol during this study is prohibited.

Patients should be advised not to drive a car or operate dangerous machinery until they understand how TEV-50717 affects them.

Use of illicit drugs is prohibited from the time of signing of the informed consent/assent form and throughout study participation.

Patients may not donate blood from the time of informed consent/assent, while taking the IMP, and for 14 days after the last dose.

5.3. Prior and Concomitant Therapy or Medication

Any prior or concomitant therapy, medication, or procedure a patient has had within 3 months before IMP administration and up to the end of the study period, including follow-up, will be recorded on the CRF. Generic or trade name, indication, and dosage will be recorded. The sponsor will encode all therapy and medication according to the World Health Organization drug dictionary.

At each clinic visit after the screening visit, the investigator will ask patients whether they have taken any medications (other than IMP), including over-the-counter medications, vitamins, or herbal or nutritional supplements, since the previous visit. Parents/patients will be instructed during the course of the study to notify the investigator if any new medication is prescribed, including over-the-counter medications. Any prescribed medication should be reviewed with the investigator. Indication, dosage, and start and end dates should be entered on the CRF.

Medications that are allowed, provided that conditions outlined in the table are met, are shown in Appendix A, [Table 5](#).

The medical monitor must be contacted if a patient is receiving (or has to begin or stop receiving during the study) a medication that is associated with QTc prolongation or that is a known strong CYP inhibitor. Addition of a strong CYP inhibitor is prohibited.

Prohibited medications that are associated with QTc prolongation are listed in Appendix A, [Table 6](#), while prohibited antipsychotic drugs are listed in Appendix A, [Table 7](#).

5.4. Procedures for Monitoring Patient Compliance

The investigator will be responsible for monitoring patient compliance. A check of IMP compliance will be performed during each visit after the initial dispensation of IMP, and IMP accountability records will be completed. If the investigator or the sponsor determines that the patient is not in compliance with the study protocol, the investigator and the sponsor should determine whether the patient should be withdrawn. The IEC/IRB should be notified as required by national and local regulations.

5.5. Dose Reduction and Temporary IMP Discontinuation

Dose Reduction

If a patient experiences a “clinically significant” adverse event that is attributed to IMP, the investigator will determine if a dose reduction or suspension is necessary. Dose adjustments should be made based on all available information, including the patient and caregiver/adult reports of adverse events and tic reduction, the clinical assessment of safety and efficacy by the investigator, and information from rating scales. **If more than 1 dose reduction is required for an adverse event, the medical monitor must be notified.**

If the determination that a patient requires a dose reduction or suspension is made during a telephone contact, an unscheduled clinic visit should be conducted as soon as practicable thereafter.

Dose Suspension

Suspension of study medication for up to 1 week, if warranted for patient safety, is allowed. If the patient restarts study medication within 7 days of suspension, the full dose of TEV-50717 may be resumed without titration. **Suspensions of study medication for adverse events must be reviewed with the medical monitor before therapy is restarted.** If a subject’s serum potassium or magnesium were tested and found to be below the lower limit of normal and clinically significant, the laboratory test should be repeated at least once. If the abnormality in the repeated laboratory test is consistent with the prior laboratory test, the IMP must be suspended. The Medical Monitor must be contacted to determine the appropriate investigation and treatment. TEV-50717 may only be restarted once serum potassium or magnesium have normalized.

The reason for a dose reduction or suspension must be clearly documented.

If a dose reduction or suspension occurs before a scheduled clinic visit, the clinic visit will be postponed so that efficacy evaluations can be performed at least 5 days after the change.

The patients who restart IMP treatment will follow the visit schedule as outlined in [Table 1](#).

Patients who withdraw from the study will proceed as described in Section [4.4](#).

5.6. Total Blood Volume

The total volume of blood to be collected for each patient in this study is approximately 35 mL, as detailed in [Table 3](#).

Table 3: Blood Volumes

Type of samples	Volume per sample	Total number of samples	Total volume
Clinical laboratory (chemistry/hematology)	10 mL	2	20 mL
Pharmacokinetic	5 mL	1 time point (week 12) × 2 samples	10 mL
CYP2D6 genotyping	3 mL	1	3 mL
Optional pharmacogenetic sample	2 mL	1	2 mL
Total			35 mL

CYP2D6=cytochrome P450 2D6.

Note: beta human chorionic gonadotropin testing (in females who are postmenarchal or ≥ 12 years of age) is included in the clinical laboratory sample.

6. ASSESSMENT OF EFFICACY

Site-administered efficacy scales include the YGTSS and the [REDACTED], and self-administered efficacy scales include the TS-PGII, [REDACTED] and C&A-GTS-QOL.

6.1. Primary Efficacy Measure and Justification

The primary efficacy measure is the TTS of the YGTSS.

The YGTSS is administered at screening; baseline; and weeks 2, 4, 6, 9, 12, and 13:

- Complete assessment (Checklist and Severity Ratings) at screening, baseline, and weeks 4 and 12
- Severity Ratings assessment only at weeks 2, 6, 9, and 13
- Input from caregiver/adult is required for all patients irrespective of age.

The choice of YGTSS (specifically the TTS) as a primary efficacy measure is supported by its wide use in clinical practice for evaluation of symptoms associated with TS and its successful use in the Phase 1b study SD-809-C-17 (Section 1.3.2.2).

The YGTSS rating scale is a semi-structured clinician rating instrument that provides an evaluation of the number, frequency, intensity, complexity, and interference of motor and phonic tics (Leckman et al 1989). The items pertaining to the tic ratings are scored on 2 subscales: Motor Tics and Vocal Tics. Behaviors are rated on a 6-point scale. The scale has a look-back period of 1 week. Additionally, the scale assesses the severity of tics, which includes overall impairment of the patient, and combines motor and visual tic information into a TTS score. A [REDACTED] can then be determined by combining the patient's severity rating with the TTS.

A reference sample is provided in [Appendix G](#).

6.2. Key Secondary Efficacy and Exploratory Measures

6.2.1. Tourette Syndrome—Clinical Global Impression

The TS-CGI is administered at baseline and at weeks 2, 4, 6, 9, 12, and 13. The TS-CGI scale is a 7-point Likert scale that allows the clinician to use all available information to assess the impact of tics on the patient's quality of life. The TS-CGI is rated as follows: 1 (normal), 2 (borderline), 3 (mild), 4 (moderate), 5 (marked), 6 (severe), and 7 (extreme).

A reference sample is provided in [Appendix H](#).

6.2.2. Tourette Syndrome—Patient Global Impression of Impact

The TS-PGII is administered at baseline and weeks 2, 4, 6, 9, 12, and 13. Input from the caregiver/adult is permitted.

The TS-PGII is a single-item questionnaire that asks the patient to assess the degree of impact due to current tics. The TS-PGII uses a 5-point scale, ranging from not at all (1) to very much (5), to assess overall response to therapy. In general, patient-rated global measures of

change have face validity and have been shown to correlate with disability for a number of chronic conditions.

6.2.3. [REDACTED]

[REDACTED]

[REDACTED]

[REDACTED]

6.2.4. Child and Adolescent Gilles de la Tourette Syndrome-Quality of Life Scale

The C&A-GTS-QOL is administered at baseline, week 6, and week 12. Children 13 years of age and under may be interviewed separately or jointly with the caregiver/adult as appropriate or defined by the scale. For children over 13 years of age, caregiver/adult involvement is strongly encouraged. Questions should be directed to the child, but the caregiver/adult should be encouraged to add relevant information.

The C&A-GTS-QOL is a 27-item questionnaire specific to TS patients that asks the patient to assess the extent to which their quality of life is impacted by their symptoms. The C&A-GTS-QOL contains 6 subscales (cognitive, coprophenomena, psychological, physical, obsessive-compulsive, and ADL) and uses a 5-point Likert scale ranging from no problem to extreme problem. Patients will also be asked how satisfied they feel overall with their life at that moment by using a VAS scale between 0 and 100 (Su et al 2017).

A reference sample is provided in [Appendix K](#).

6.2.5. [REDACTED]

[REDACTED]

6.2.6. [REDACTED]

[REDACTED]

[REDACTED]

[REDACTED]

6.2.7.

7. ASSESSMENT OF SAFETY

In this study, safety will be assessed by qualified study personnel by evaluating the following: reported adverse events, clinical laboratory test results, vital signs measurements, ECG findings, physical examination findings (including body weight and height measurements), use of concomitant medication, neurological examination, C-SSRS, and CDI-2.

7.1. Adverse Events

7.1.1. Definition of an Adverse Event

Any untoward medical occurrence in a patient or clinical investigation subject administered a pharmaceutical product and which does not necessarily have to have a causal relationship with this treatment.

An adverse event can, therefore, be any unfavorable and unintended physical sign, symptom, or laboratory parameter that develops or worsens in severity during the course of this study, or significant worsening of the disease under study or of any concurrent disease, whether or not considered related to the IMP (TEV-50717). A new condition or the worsening of a pre-existing condition will be considered an adverse event. Stable chronic conditions (such as arthritis) that are present before study entry and do not worsen during this study will not be considered adverse events.

Accordingly, an adverse event can include any of the following:

- intercurrent illnesses
- physical injuries
- events possibly related to concomitant medication
- significant worsening (change in nature, severity, or frequency) of the disease under study or other pre-existing conditions (Note: A condition recorded as pre-existing that is intermittently symptomatic [eg, headache] and that occurs during this study should be recorded as an adverse event.)
- drug interactions
- events occurring during diagnostic procedures or during the washout phase of this study
- laboratory or diagnostic test abnormalities that result in the withdrawal of the patient from the study, are associated with clinical signs and symptoms or a serious adverse event, or require medical treatment or further diagnostic work-up, or are considered by the investigator to be clinically significant (Note: Abnormal laboratory test results at the screening visit that preclude a patient from entering the study or receiving study treatment are not considered adverse events.)

7.1.2. Recording and Reporting Adverse Events

For recording of adverse events, the study period is defined for each patient as that time period from signature of the informed consent/assent form to the end of the follow-up period. For this study, the follow-up period for recording of adverse events is defined as 1 week of washout for patients who will participate in the open-label safety extension study TV50717-CNS-30047 and 2 weeks after the last dose of IMP for patients who will not roll over into Study TV50717-CNS-30047.

All adverse events that occur during the defined study period must be recorded both on the source documentation and the CRF, regardless of the severity of the event or judged relationship to the IMP. For serious adverse events, the Serious Adverse Event Form must be completed, and the serious adverse event must be reported immediately (see Section 7.1.5.3.1). The investigator does not need to actively monitor patients for adverse events after the defined period. Serious adverse events occurring to a patient after the treatment of that patient has ended should be reported to the sponsor if the investigator becomes aware of them, following the procedures described in Section 7.1.5.3.1.

At each contact with the patient, the investigator or designee must question the patient about adverse events by asking an open-ended question such as, “Have you had any unusual symptoms or medical problems since the last visit? If yes, please describe.” All reported or observed signs and symptoms will be recorded individually, except when considered manifestations of a medical condition or disease state. A precise diagnosis will be recorded whenever possible. When such a diagnosis is made, all related signs, symptoms, and any test findings will be recorded collectively as a single diagnosis on the CRF and, if it is a serious adverse event, on the Serious Adverse Event Form.

The clinical course of each adverse event will be monitored at suitable intervals until resolved, stabilized, or returned to baseline; until the patient is referred for continued care to a health care professional; or until a determination of a cause unrelated to the IMP or study procedure is made.

The onset and end dates, duration (in case of adverse event duration of less than 24 hours), action taken regarding IMP, treatment administered, and outcome for each adverse event must be recorded both on the source documentation and the CRF.

The relationship of each adverse event to IMP and study procedures, and the severity and seriousness of each adverse event, as judged by the investigator, must be recorded as described below.

Further details are given in the safety monitoring plan.

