Patients who complete the study may be eligible to begin participation in an open-label safety extension study (TV50717-CNS-30047) after the end of the washout period. At the week 13 visit, patients may choose to enter Study TV50717-CNS-30047 (on that day), or they will have an additional week to make a decision and return for day 1. Patients not participating in Study TV50717-CNS-30047 will have a follow-up telephone contact to evaluate safety 1 week after the end of the washout period (2 weeks after their last dose of IMP).

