3.1.5. Washout Period and Follow-up

[figure not shown]
All patients will discontinue IMP at the week 12 visit and will return 1 week later for evaluation of safety and tic reduction (week 13). Patients who complete the study may be eligible to begin participation in the open-label safety extension study TV50717-CNS-30047. For this study, the follow-up period is defined as 1 week of washout for patients who will participate in the open-label safety extension study TV50717-CNS-30047 and 2 weeks after the last dose of IMP (1 week after the end of the washout period) for patients who will not roll over into the open-label safety extension study TV50717-CNS-30047. At the week 13 visit, patients may choose to enter Study TV50717-CNS-30047 (on that day), or they will have an additional week to make a decision and return for day 1. Patients not participating in Study TV50717-CNS-30047 will have a follow-up telephone contact to evaluate safety 1 week after the end of the washout period (2 weeks after their last dose of IMP).

Prohibited drugs will remain the same during the washout period for patients who will participate in the open-label extension study TV50717-CNS-30047.

Patients who will not participate in the extension study (Study TV50717-CNS-30047) may begin/resume tic therapy medication after the first week of the washout period.

See [Table 1](#) for study procedures and assessments.

See [Figure 1](#) for study schema.

Figure 1: Overall Study Schema

^a Maximum total daily dose for patients ≥40 kg is 48 mg/day (24 mg bid), 30 to <40 kg is 42 mg/day (21 mg bid), and 20 to <30 kg is 30 mg/day (15 mg bid). For those considered CYP2D6 impaired, maximum daily dose for patients ≥40 kg is 36 mg/day, 30 to <40 kg is 24 mg/day, and 20 to <30 kg is 18 mg/day (Table 2).

^b If a stable dose is reached before the indicated time, the patient should continue taking that dose for the remainder of the titration period and throughout the maintenance therapy dosing.

^c This is a telephone contact for safety evaluation, required only for patients who will not roll over into the open-label safety extension study TV50717-CNS-30047.

bid=twice a day; CYP=cytochrome P450; ET=early termination visit.

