Assess IMP accountability/compliance/supply			X ^z	X	X			X ^j						
Assess adverse events	X	X	X	X	X	X	X	X	X	X	X	X	X	X
Concomitant medications ^{aa}	X	X ^{aa}	X ^{aa}	X ^{aa}	X ^{aa}	X ^{aa}	X ^{aa}	X ^{aa}	X ^{aa}	X ^{aa}	X ^{aa}	X ^{aa}	X ^{aa}	X ^{aa}

^a The baseline visit will occur on the same day as the scheduled first dose of the IMP (day 1).

^b Assessment to occur at the end of the study week.

^c Patients will be provided with a diary to record critical information on dosing. The date and time of the last dose of study medication before the week 12 visit should be recorded in the diary by the patient or caregiver/adult. The site will document the date and time of the sample collection. Prior to the clinic visit on week 12, patients will be reminded to record the start time of their last meal and the time of their last dose in their diary.

^d For patients who withdraw prematurely, an early termination visit should be conducted as soon as possible after the last dose of IMP. All patients who discontinue early will have a follow-up telephone contact for safety evaluation 2 weeks after their last dose of IMP; evaluations will be as described for week 14 (Section 3.13.4.2).

^e This visit is a telephone contact for safety evaluation, required only for patients who will not roll over into the open-label safety extension study TV50717-CNS-30047.

^f The screening visit may be conducted over 2 separate visits at the discretion of the investigator.

^g Dose adjustment will be made by the investigator after telephone contact with the patient and caregiver/adult to evaluate tic reduction and adverse events.

^h Weight must be measured with shoes and outerwear off. Before pulse and BP are measured, the patient must be in a supine or semi-erect/seated position and resting for at least 5 minutes (the same position and arm should be used each time vital signs are measured for a given patient).

ⁱ Orthostatic BP and pulse will be measured after patient is in a standing position for at least 3 minutes.

^j Assessment to be completed at investigator's discretion.

^k All ECGs will be performed after at least 5 minutes rest in a supine or semi-supine position.

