### **9.4. ADVERSE EVENTS**

Adverse events will be collected and recorded from the time a patient signs the informed consent to the end of follow-up period. For this study, the follow-up period for recording of adverse events is defined as 1 week of washout for patients who will participate in the open-label safety extension study TV50717-CNS-30047 and 2 weeks after the last dose of IMP for patients who will not roll over into Study TV50717-CNS-30047.

For all AEs, preferred AE terms and system organ class (SOC) will be coded using terminology from the Medical Dictionary for Regulatory Activities (MedDRA), version 20.1 or higher.

A treatment emergent adverse event (TEAE) is defined as an AE that begins after the first administration of study medication or existing AEs that worsen after the first dose of study medication. All reported AEs will be listed, but only TEAEs will be summarized in tables.

Drug related AEs will be considered those to be reasonable possibility based on the investigators assessment. Missing relationship will be considered as “Related”.

Unless otherwise specified, AEs will be summarized by SOC and PT, with SOCs and PTs within SOCs presented in descending order of patient incidence.

AE summary tables are listed below:

- An overall summary of the number and percentage of patients reporting any TEAEs, serious TEAEs, treatment-related TEAEs, serious treatment-related TEAE, any TEAEs leading to study drug discontinuation, any TEAEs leading to patient study drug interruption, and TEAEs leading to death. The overall summary will also be prepared by age group (6-11 years, or 12-16 years);
- TEAEs overall and by SOC and PT;
- TEAEs by severity, overall and by SOC and PT. Missing severity, if any, will be assumed as “severe”;
- Serious TEAEs, overall and by SOC and PT;
- Serious treatment related TEAEs, overall and by SOC and PT
- TEAEs by relationship to study treatment, overall and by SOC and PT;
- TEAEs leading to study drug discontinuation, overall and by SOC and PT;
- TEAEs leading to study drug interruption, overall and by SOC and PT;
- TEAEs leading to dose reduction overall and by SOC and PT;
- Most common TEAEs, overall and by PT. Most common TEAEs are defined as TEAEs that occur in > 4% of the patients in either of the treatment groups;
- SMQs for suicide/self-injury, depression (exclude suicide and self-injury), and Parkinson-like events.

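### For completers who take the extra week after week 13 and then enter the extension, the protocol requires no routine recording of new non-serious adverse events on off-drug days 8 to 14

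*Protocol*

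**What the plan says.** Protocol 3.1.5 fixes the end of treatment and the next visit: "All patients will discontinue IMP at the week 12 visit and will return 1 week later for evaluation of safety and tic reduction". That visit is week 13.

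Protocol 3.1.1 and 3.1.5, repeated in SAP 3.3, give two routes into the extension. Patients may enter on the day of the week 13 visit, or "or they will have an additional week to make a decision and return for day 1".

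Protocol 7.1.2 sets the recording period by the route taken: "1 week of washout for patients who will participate in the open-label safety extension study TV50717-CNS-30047", and 2 weeks after the last dose for the others. SAP 9.4 repeats the split, with the longer window given as "2 weeks after the last dose of IMP for patients who will not roll over into Study TV50717-CNS-30047".

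The week 14 telephone contact in Protocol Table 1 (footnote e) is "required only for patients who will not roll over into the open-label safety extension study"; Protocol 3.13.4.2 agrees. Beyond the window, Protocol 7.1.2 states: "The investigator does not need to actively monitor patients for adverse events after the defined period". Two duties continue. Serious events are reported if the investigator becomes aware of them, and events already recorded are followed to resolution, stabilization or another listed end point.

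**The concern.** The recording window depends on whether the patient will join the extension, but the protocol lets the patient settle that after the shorter window has closed. A late entrant is off drug for a second week and not yet in the extension, with no scheduled safety contact in this study during that week. Every other completer has either moved into the extension by then or is covered to week 14. Patients who discontinue early get a call 2 weeks after their last dose (Protocol 3.13.4 and 4.4).

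At stake is the completeness of off-drug safety data in children, for one subgroup. A second issue follows in the tables. SAP 9.4 summarizes follow-up-period events as percentages of the safety analysis set, so patients with 7 and with 14 days of observation share one denominator. Which window a patient gets depends on a choice made after randomization.

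**Working it through.** The documents give no figure of their own to reproduce. The check is a day count on planned days.

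Inputs:

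- Week 12, last dose: Day 84 (SAP Table 2).
- Week 13 visit: Day 91 (Protocol Table 1, SAP Table 2).
- Week 14 call: Day 98 (same tables).
- Latest extension entry: one week after week 13, so about Day 98 (Protocol 3.1.1 and 3.1.5).

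Windows:

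- Patients who roll over: 91 − 84 = 7 days.
- Completers who do not: 98 − 84 = 14 days.
- Uncovered span for a late entrant: up to 98 − 91 = 7 days, which is 7/14 = 50% of the longer window.
- Off-drug days concerned: 92 − 84 = 8 to 98 − 84 = 14.

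| Group | Routine recording ends | Enters extension or is called | Uncovered days |
|---|---|---|---|
| Enters at week 13 | Day 91 | Day 91, entry | 0 |
| Enters after the extra week | Day 91 | up to about Day 98, entry | up to 7 |
| Completes, does not enter | Day 98 | Day 98, call | 0 |
| Discontinues early, last dose on day L | L + 14 | L + 14, call | 0 |

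Only the second row has a gap. With k late entrants the total is at most 7k patient-days. The documents give no roll-over or delay rate, so k cannot be derived. Actual days move with the ±3-day visit windows.

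The gap lies in collection, not in analysis. The SAP 6.4 follow-up period runs to the end of the study, and the definition of a treatment-emergent event in SAP 9.4 has no upper time limit. An event in these days would be counted if it were recorded.

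The protocol's summary of changes suggests a likely origin. Amendment 03 introduced the extra week in 3.1.1 and names 3.1.5 as also affected, but not 7.1.2. This is background only; the mismatch stands in the current text.

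**The case against.** The strongest reply is that the 1-week rule need not apply. It covers patients who will participate, and an undecided patient is not yet one of them, so a site may keep the 2-week window open. The extra week ends at about Day 98, when the week 14 call is due, so the patient is either seen for extension day 1 or telephoned. Protocol 7.1.2 also requires an adverse-event question at every contact, covering the time since the last visit. This stands in part: a careful site could close the gap. But the protocol does not tell it to. Once the patient has entered, the wording places the event outside this study's recording period.

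A reader might infer that no adverse events are collected in that week. The documents do not support this. Passive reporting of serious events and follow-up of ongoing events continue, and under Protocol 7.9 families are instructed to report depressive or suicidal symptoms immediately.

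A reader might also infer that the events are lost. That would require the extension to start collection on its own day 1 without asking about the preceding days. The extension protocol is not among these documents, so this is not shown.

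It is also fair to say that the first off-drug week is well observed. Week 13 is an in-clinic visit with adverse-event questioning, vital signs and the depression and suicidality scales. Patients who do not enter may resume tic medication after that week, so their days 8 to 14 are not a clean untreated comparison. This limits the weight of the point but does not remove the gap.

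On the table, the unequal windows are a consistently stated rule and the summary is descriptive, with no between-arm test. That is correct, and it is why the table change is an improvement in presentation and not the repair of an error.

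**Conclusion.** The point holds in a narrow form. For completers who use the extra week and then enter the extension, up to 7 off-drug days (about Days 92 to 98) carry no requirement in this study for routine recording of new non-serious events. No rule covers a patient who is undecided at week 13.

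This rests on planned visit days and on applying the 1-week rule to anyone who eventually enters. The number of patients is unknown, and the extension may capture the events.

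A reader might go further and infer that the two arms are observed for different lengths of follow-up. No roll-over rate by arm is given, so no such difference can be put in numbers. If there were one, it would come mainly from the general split between entrants and non-entrants and would exist even if nobody used the extra week. What can be said is that the follow-up table mixes 7-day and 14-day observation over one safety-set denominator.

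The point is minor. No efficacy result is affected.

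**What to change.** - Reconcile Protocol 3.1.1, 3.1.5, 7.1.2 and Table 1 footnote e with SAP 9.4. Define the recording period for extension entrants as running until extension day 1, and ask the adverse-event question at that visit. This also settles the undecided patient: recording stays open until the patient either enters or reaches the week 14 call. If the extension protocol already collects these days, a cross-reference to it would close the collection gap.
- In SAP 9.4, present follow-up-period events by arm for the first 7 days after the last dose and list later events separately. That window is common to all patients nominally, subject to the visit windows. State that it is anchored on the last dose, because the SAP 6.4 period boundaries can fall at an early termination visit instead.

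The cost is a short wording change, one question at a visit the patient attends anyway, and a split descriptive table. The drawback of the split is that events after day 7 move from the by-arm table to a listing.
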